8.2.6 HANDLING OF UNRESOLVED ADVERSE EVENTS

- If any AE is present when a Subject completes the Study or if a Subject is prematurely withdrawn from the Study, an attempt will be made to follow the Subject up for 12-weeks. Amongst the AEs ongoing on the last Study visit as per the Study protocol, all the AEs have to be recorded in the AE form
- The Investigator assesses the status of the AEs
- The AEs recorded at the time of exit are to be followed until,
 - The AEs are considered to become stable as per the Investigator's discretion, or
 - The AEs are no longer considered to be medically significant by the Investigator, or
 - The database of the Study is declared to be locked
- The sponsor reserves the right to ask further information on any AE/SAE, which may be considered of interest

8.2.7 EVENT NOT TO REPORTED AS AE

Progression of underlying disease (at Investigator's discretion) / Study indication/lack of efficacy of the IP would NOT be reported as an AE/SAE.

8.2.8 SERIOUS ADVERSE EVENT REPORTING

- Any SAE occurring during the course of the Study would be treated by established standards of care to protect the life and health of the Subject
- Any SAE, irrespective of causality, must be immediately notified to the safety team at the CRO and the Sponsor. It must be followed up within 24 hours on the Study specific SAE reporting form with as much detailed information regarding the event that is available
- Investigators would not wait to receive additional information to fully document the event, before notifying SAE to the CRO.
- The SAE reporting form should detail all relevant aspects of the AEs in question. Where applicable, information from relevant hospital case records and autopsy reports would be obtained and provided, in a blinded fashion, to the CRO.
- All SAEs would be reported within 24 hours of Investigator's knowledge of the event to the CRO. and to the respective EC and Regulatory authorities (CDSCO) by the Investigator as soon as possible as per applicable regulations. The Investigator site and the sponsor would have to copy all SAE related communications on [contact] while communicating with the CRO and [contact] for communicating with the Sponsor. The SAE forms should be shared via E-mail as scanned attachments
- The event must also be recorded on the CRF AE page
- The follow up SAE form also should be filled and sent to the CRO, the Sponsor, CDSCO and EC within 24 hours of updated information on SAE
- Communicate filled CIOMS-I MedWatch form within 14 calendar days to CDSCO

The CRO does not prefer Fax as the mode of communication for SAEs. However, if a site would insist on using fax then the site should have to send an email stating the information that the fax has been sent. In the event of any technical issue wherein the site would not be able to send the

Email, then a phone call should be made to the concerned medical monitor to inform that SAE form sent via fax.

Fax: [name]

All the events will be monitored by the Investigator until the event has subsided or, in a case of permanent impairment, until the event stabilizes and the overall clinical outcome has been ascertained.

8.2.9 REPORTING EVENTS TO PARTICIPANTS

Not-applicable

8.2.10 EVENTS OF SPECIAL INTEREST

Not-applicable

8.2.11 REPORTING OF PREGNANCY

In event of a pregnancy during the Study, the same is required to be reported to the CRO safety team immediately via telephone and in the form of Pregnancy Report Form (PRF) within 24 hours from the knowledge of the Investigator about the pregnancy. The Subject would be discontinued from the Study and the End of Study visit procedure would be completed.

A Pregnancy Outcome form (POF) will then be sent to the site from the CRO/the Sponsor, which should be filed and a copy of which will be faxed back to the CRO/the Sponsor safety team within 24 hours from the knowledge of the pregnancy reaching its outcome

Pregnancy during a clinical trial itself is not regarded as an AE/ SAE unless pregnancy falls in the following types:

- Ectopic pregnancy
- Molar pregnancy
- The concerned pregnancy results in one of the following outcomes:
 - Miscarriage/late spontaneous abortion
 - Stillbirth
 - Congenital Malformation/Anomaly
 - Neonatal death (within 28 days from birth)
 - Infant death (after 28 days from birth but assessed as related to the IP by the Investigator)

In case for any pregnancy reported during a clinical trial, results in one of the above outcomes, the Investigator is required to fill the AE form and the corresponding SAE form and report to the CRO/the Sponsor safety team within same timelines as mentioned above.

8.2.12 EXPEDITED SAFETY REPORTING

Any serious AE, which is unexpected and at least possibly related to the IP calls for expedited reporting to the regulatory authorities and the ECs as per CDSCO requirements.

As the CRO acts on behalf of the Sponsor, the regulatory reporting time clock starts when any member of the CRO safety team qualifies a SAE as an expedited SAE, in consultation with the Sponsor.

8.2.13 DEFINITION OF UNANTICIPATED PROBLEMS (UP)

Not-applicable

8.2.14 UNANTICIPATED PROBLEM REPORTING

Not-applicable

8.2.15 REPORTING UNANTICIPATED PROBLEMS TO PARTICIPANTS

Not-applicable

9 STATISTICAL CONSIDERATIONS

9.1 STATISTICAL HYPOTHESES

Primary Efficacy Endpoint(s):

Proportion of Subjects achieving Target Ulcer closure within 12-week Treatment Phase, as assessed by blinded Investigator.

Secondary Efficacy Endpoint(s):

- Time to Target Ulcer Closure during the 12-week Treatment Phase, as assessed by the blinded Investigator
- Proportion of Subjects achieving Target Ulcer Closure till End of study, as assessed by the blinded Investigator

9.2 SAMPLE SIZE DETERMINATION

This Study will have FAS Population (Efficacy Evaluable Population) of minimum of 240 Subjects (minimum of 120 each in Group 1 and Group 2). To ensure this and assuming 20% drop out rate, the population of two groups would be up to 300 Subjects. For safety analysis of Vehicle of Galnobax®, maximum of 50 Subjects will be recruited in Vehicle plus SoC group. Thus, overall population of maximum of 350 Subjects will be recruited in the Study.

Sample Size Determination and Rationale:

The sample size calculation has two components. One is based on statistical power and the other is based on clinical judgment.

The sample size calculation is based on the primary endpoint for the Study that is proportion of Subjects achieving complete closure of Target Ulcer within 12-week Treatment Phase, as determined by blinded Investigator's assessment.

The sample size is obtained based on the assumption that there will be a clinically meaningful difference of 21%, (i.e., 39% of SoC vs 60% of Galnobax®-treated achieved complete closure of Target Ulcer, odds ratio of 0.65). This assumption is based on the following:

- a. Literature reports from various DFU trials showed that average percent wounds closed using SoC treatment is 24% globally.^{5 27} However, percent wounds closed using SoC treatment in recently completed DFU trial in India is reported to be 37.8%.²⁸ In view of this, it is assumed that 39% wounds may close in the SoC group.
- b. In Phase 1/2 study of Galnobax®, 60% wounds closed within 12-week of Galnobax® treatment. Furthermore, 67% wounds were closed in Galnobax® arm for wounds with wound age > 6 weeks. In view of this, the inclusion criterion is revised to include Subjects with wounds of at least 6 weeks (which was 4 weeks in Phase 1/2 study) and it is assumed that 60% wounds may close in the Galnobax® treatment group.

To meet the Type I error rate of 0.05 (95% confidence interval), 2-sided analysis and 90% power, 120 Efficacy Evaluable Subjects in Group 1 and Group 2 will be required for making the FAS Population in the Study as 240. To accommodate the potential drop outs rate of 20%, a total of 300 Subjects will be randomized in these Groups to ensure more than 90% power for the primary endpoint analysis (i.e., proportion of Subjects achieving Target Ulcer Closure within 12-week Treatment Phase).

The safety evaluation of Vehicle of Galnobax® will be done by recruiting population of 50 Subjects in the Vehicle plus SoC group. As there is not hypothesis testing or statistical comparison proposed for this arm, this population might not be statistically significant, but would enough to give reasonable estimate of safety for Vehicle of Galnobax®.

9.2.1 RANDOMIZATION AND STRATIFICATION OF STUDY POPULATION:

Prior to randomization, Subjects will be stratified by location of Target Ulcer (planter or non-planter), and the Target Ulcer size ($<5\text{ cm}^2$ or $\geq 5\text{ cm}^2$). The randomization will be done at the ratio of 3:3:1 in one of the following groups, using an IWRS:

- Galnobax® 14% plus SoC or
- SoC or
- Vehicle plus SoC

9.3 POPULATIONS FOR ANALYSES

For this Study, analysis will be done on ITT Population (Safety Evaluable Population), FAS Population (Efficacy Evaluable Population) and PP Population.

The ITT Population i.e. Safety Evaluable Population will include all those Subjects who are randomized and received at least one dose of the study treatment.

The FAS Population (Efficacy Evaluable Population) will include all randomized Subjects who has had at least six weekly assessments for Target Ulcer Closure or has Target Ulcer closed earlier than six weeks.

The PP Population will include all randomized Subjects who have completed the Study without any major protocol deviation.

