10.4	Protocol Amendment History	56
11	APPENDICES.....	57
12	REFERENCES	64

List of Tables

Table 1 Subject progression as per condition of Target Ulcer.....	17
Table 2 Dosing schedule	18
Table 3 Composition of Galnobax®	22
Table 4 Labelling information of Galnobax®	25
Table 5 Assessment of Intensity	38
Table 6 List of Abbreviations.....	54

Definitions

Term	Definition
Diabetic Foot Ulcer (DFU)	Diabetic foot ulceration is full-thickness penetration of the dermis of the foot in a person with diabetes.
Standard of Care (SoC)	Wound cleaning by normal saline, maintenance of moist wound environment and off-loading of the Target Ulcer. In addition, during Site Visits removal of necrotic, infected and/or nonviable tissue by debridement and management of infection to be done by the Investigator, if required.
Target Ulcer Closure	100% re-epithelialization without drainage or dressing requirement (except if recommended by the Investigator for covering of the closed wound) to be confirmed by two consecutive site visits two weeks apart from first observation of closure.
Time to Target Ulcer Closure	Duration of first observation of closure from Baseline visit for those Target Ulcers for which conditions for Target Ulcer Closure were satisfied.
Intent to Treat (ITT) Population (Safety Evaluable Population)	All Subjects who are randomized and received at least one dose of Study medication will be included in ITT Population.
Full Analysis Set (FAS) Population (Efficacy Evaluable Population)	All randomized Subjects who had at least 6 weekly Site Visits for the assessments of Target Ulcer Closure or had Target Ulcer closed earlier than 6 weeks.
Per Protocol (PP) Population	All randomized Subjects who have completed the Study without any major protocol deviation.

STATEMENT OF COMPLIANCE

The trial will be conducted in accordance with International Council for Harmonization Good Clinical Practice (ICH GCP), Declaration of Helsinki and GCP guidelines as per Central Drugs Standard Control Organization (CDSCO), Directorate General of Health Services (DGHS), Government of India. The Principal Investigator will ensure that no deviation from, or changes to the protocol will take place without prior agreement from the Sponsor and documented approval from the Ethics Committee (EC), except where necessary to eliminate an immediate hazard(s) to the trial participants. All personnel involved in the conduct of this Study have completed Human Subjects Protection and ICH GCP Training.

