4.2 SCIENTIFIC RATIONALE FOR STUDY DESIGN

The Study consists of about one week (7 to 10 days) of Screening period to confirm the suitability of Subject for the Study and to restrict recruitment of Subjects having healing ulcers. The Study has Treatment Phase of up to 12-weeks (84 ± 3 days) or the Target Ulcer Closure, whichever happens earlier as the Investigational Product (IP) requires 12-weeks of treatment to establish its efficacy. In view of this, if the Target Ulcer re-opens within these 84 days, the Subject will resume the treatment, up to completion of the Treatment Phase or the Target Ulcer Closure, whichever is earlier. If Target Ulcer closes prior to 12-week, then the Subject enters the 12-week Follow-Up phase immediately. The 12-week Follow-Up is required to confirm Target Ulcer closure, assess strength of closed Target Ulcer, assess progression of open wounds post Treatment Phase in terms of wound size and AEs, if any.

In this trial, Subjects will be randomized in three Groups viz, Galnobax® plus SoC, only SoC, and Vehicle plus SoC in 3:3:1 ratio. A large population is required to achieve statistically significant efficacy endpoint for wound closure, whereas relatively smaller number of Subjects are sufficient to assess non-deleterious effects of Vehicle gel. During randomization, the Subjects will be stratified based on location as well as size of the Target Ulcer to have a proportional population in the three groups. Since SoC only is the treatment of choice used in clinical setting for DFU presently, this trial uses SoC only as comparator arm to Galnobax® plus SoC treatment for efficacy analysis. The parameters of Vehicle plus SoC arm will be compared with only SoC arm to check if Vehicle has any deleterious effects on wound healing.

The FAS Population (Efficacy Evaluable Population) will include all randomized Subjects who have at least 6 weekly assessments for Target Ulcer Closure or has Target Ulcer closed earlier than 6 weeks. The efficacy analysis in this Study will use FAS Population in order to ensure that Subjects have received reasonable treatment, and are assessed for Target Ulcer Closure by blinded Investigator.

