7 STUDY INTERVENTION DISCONTINUATION AND PARTICIPANT DISCONTINUATION/WITHDRAWAL

7.1 DISCONTINUATION OF STUDY INTERVENTION

The subjects that report Osteomyelitis, cellulitis or SAE/AE where study intervention cannot be given, should be discontinued. For all discontinued Subjects, maximum possible and relevant Study information shall be gathered and be described in the source. This information can be gathered at Site visit or telephonically. If the discontinuation happens during the Treatment /Follow up Phase, the last visit prior to discontinuation will be treated as EOT/EOS visit and corresponding CRF will be completed by the Investigator.

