7.2 PARTICIPANT DISCONTINUATION/WITHDRAWAL FROM THE STUDY

Participants are free to withdraw from participation in the Study at any time. If the withdrawal happens during the Treatment /Follow up Phase, the last visit prior to withdrawal will be treated as EOT/EOS visit and corresponding CRF will be completed by the Investigator.

Subjects who sign the informed consent form (ICF) and are randomized but do not receive the study intervention will not be replaced and will not be part of ITT Population.

Subjects who sign the ICF, and are randomized and receive the study intervention, and subsequently withdraw, or are withdrawn or discontinued from the study, will not be replaced and yet be part of ITT Population.

Subjects must be discontinued from the Study after randomization if any of the following events occur (Stopping or Discontinuation Rules for Individual Subjects):

1. A Subject withdraws consent
2. Investigator recommends that the Subject should discontinue the participation in the Study
3. Subject misses two consecutive Weekly Visits during Treatment Phase
4. If the Target Ulcer and the adjoining wound merge together and if the Investigator opines that following the Target Ulcer is difficult. A detailed note by the Investigator will be recorded in the e-CRF outlining reasons for such merger in line with the preceding measurement of Target Ulcer
5. If Subject requires hospitalization for more than two consecutive weeks during the Study
6. The Subjects with treatment compliance of less than 80% or more than 120% during the week, will be considered treatment non-compliant for that week. If such non-compliance is observed for more than three weeks, and if the blinded Investigator opines that it may affect the outcome of the Study, then the Subject shall be considered non-compliant for the Study and shall be discontinued from the Study
7. If the blinding of a Subject is compromised
8. Any form of major protocol violation
9. The Target Ulcer increases in size (more than 30%) for two consecutive weeks or requires deep, surgical debridement for more than two occasions during the Treatment Phase to address Target Ulcer deterioration
10. The Target Ulcer becomes infected requiring topical antimicrobial treatment
11. If Subject develops osteomyelitis or cellulitis during the Study on the foot having the Target Ulcer
12. If female Subject becomes pregnant, during the study
13. If Subject misses 6 consecutive dressings

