9.4 STATISTICAL ANALYSES

9.4.1 GENERAL APPROACH

Before database lock, a statistical analysis plan (SAP) will be issued as a separate document, providing the detailed methods for analyses outlined below. Any deviation from the planned analyses will be described and justified in the final integrated clinical Study report.

A maximum of 350 Subjects will be competitively recruited at 40 sites from the DFU Subject population as described in [section 4.1](#).

The number and percentage of all the DFU Subjects entering and completing the clinical Study will be provided across treatment groups. The summarization of primary reason of discontinuation will also be provided across treatment groups.

For this Study, analysis will be done on ITT Population (Safety Evaluable Population), FAS Population (Efficacy Evaluable Population) and PP Population.

The continuous data will be summarized by treatment Group using descriptive statistics (number of Subjects [n], Mean, Standard Deviation [SD], Median, Minimum and Maximum [Range]). Categorical data will be summarized by treatment group using frequency count (n) and percentages (%).

The primary and secondary efficacy analysis will be performed on all Subjects in FAS Population (Efficacy Evaluable Population) and PP Population comparing Group 1 (Galnobax® plus SoC) and Group 2 (SoC only). All the statistical analysis will be performed using SAS® version 9.4 or later.

The Safety analysis will be performed on all Subjects in ITT Population (Safety Evaluable Population).

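### The full analysis set used for the primary comparison is selected partly on outcome: early closers always enter, while unhealed subjects who leave before six weekly assessments drop out of numerator and denominator alike.

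*Combined protocol and SAP*

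**What the plan says.** Section 9.3 defines the FAS as "all randomized Subjects who has had at least six weekly assessments for Target Ulcer Closure or has Target Ulcer closed earlier than six weeks". The Definitions table gives the same rule: "All randomized Subjects who had at least 6 weekly Site Visits for the assessments of Target Ulcer Closure", or earlier closure. Section 4.2 explains the choice: "The efficacy analysis in this Study will use FAS Population in order to ensure that Subjects have received reasonable treatment".

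Section 9.4.1 states that "The primary and secondary efficacy analysis will be performed on all Subjects in FAS Population (Efficacy Evaluable Population) and PP Population". Section 9.4.2 repeats this for the primary endpoint and divides the number closed by the number of subjects in that population. The per-protocol (PP) set requires completion of the Study without a major deviation. The ITT set is assigned to safety and baseline summaries. It is not all-randomised either: section 7.2 says subjects "randomized but do not receive the study intervention will not be replaced and will not be part of ITT Population".

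Section 7.2 also lists events that require exit from the Study. Several describe a failing ulcer, for example "The Target Ulcer increases in size (more than 30%) for two consecutive weeks", infection needing topical antimicrobials, and osteomyelitis or cellulitis of the study foot. Section 9.4.9 labels a subject needing more than two surgical debridements a treatment failure, without saying how that subject enters the analysis. Section 9.4.7 leaves missing data to a separate SAP, which was not available for this review.

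**The concern.** One of the two routes into the FAS is the endpoint event itself. Take two subjects, each treated for three weeks. The one whose ulcer closes is in the FAS as a success. The one who leaves with an open ulcer is in neither numerator nor denominator. Their exposure is the same, so the reasonable-treatment rationale in section 4.2 does not explain the difference in handling.

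The subjects lost this way are not a random sample, because deterioration can itself cause exit before the sixth assessment. A treatment failure under section 9.4.9 who leaves that early is removed rather than counted.

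Removal could also differ between arms. Section 6.4 ties non-compliance to the amount of gel used, and sections 4.3 and 7.1 allow discontinuation for reactions to it; the standard-of-care (SoC) arm receives no gel. Deterioration, on the other hand, could remove more SoC subjects. The documents do not indicate which would dominate. What is at stake is the validity of the confirmatory test and the size of the reported effect.

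**Working it through.** **Inputs.** Section 9.2: closure 39% on SoC and 60% on Galnobax; two-sided 0.05; 90% power; 120 evaluable per arm; 20% drop-out; 300 randomised. Section 4.1: 3:3:1 allocation, so 150 per arm in Groups 1 and 2.

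**The plan's own figure.** n per arm = [z(0.975)·√(2p̄(1−p̄)) + z(0.90)·√(p₁(1−p₁)+p₂(1−p₂))]² / (p₂−p₁)². With p̄ = 0.495 this is (1.960×0.7071 + 1.282×0.6913)² / 0.21² ≈ 117.0, rounded up to 118, against 120 stated. Power at 120 per arm is 90.7%, and 240/0.80 = 300. The sample size reproduces; the problem is the analysis set.

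**What the rule does to a closure rate.** Let q be the proportion of all randomised subjects who close, and d the proportion removed early, none of whom closed. The FAS shows q/(1−d).

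- Equal removal, d = 20%: 31.2%/0.80 = 39% and 48.0%/0.80 = 60%. A true difference of 48.0 − 31.2 = 16.8 points is shown as 21.
- True 48.0% vs 31.2%, removal 25% Galnobax and 15% SoC: 48.0/0.75 = 64.0% and 31.2/0.85 = 36.7%, shown as 27.3 points.
- Same truth, removal 15% and 25%: 48.0/0.85 = 56.5% and 31.2/0.75 = 41.6%, shown as 14.9 points.

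**Effect on the test.** Simulation with 150 per arm and 400,000 trials per case; each subject is closed, removed early unhealed, or kept unhealed; pooled two-proportion z-test in the FAS. No true effect, 31.2% closure in both arms:

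| Removed, Galnobax / SoC | Two-sided error | Favouring Galnobax | Favouring SoC |
|---|---|---|---|
| 20% / 20% | 5.0% | 2.5% | 2.5% |
| 8% / 5% | 5.5% | 3.9% | 1.6% |
| 22.5% / 17.5% | 6.8% | 5.8% | 1.0% |
| 25% / 15% | 12.2% | 11.9% | 0.3% |
| 15% / 25% | 12.2% | 0.3% | 11.9% |

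In the same trials, a test on all randomised subjects stays at about 5.0%. With true rates of 48.0% and 31.2%, FAS power is 91% under equal 20% removal, 99% under 25/15 and 64% under 15/25.

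**Power after the fix.** Analyse all 150 per arm and count early exits as not closed. If 39% and 60% are FAS rates, the all-randomised rates are 39%×(1−d) and 60%×(1−d). Worked for d = 20%: null standard error √(2×0.396×0.604/150) = 0.0565; alternative standard error √((0.312×0.688 + 0.48×0.52)/150) = 0.0556; power = Φ((0.168 − 1.960×0.0565)/0.0556) = 84.9%.

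| Early non-closers, d | SoC | Galnobax | Power, 150 per arm |
|---|---|---|---|
| 0% (39/60 are all-randomised rates) | 39.0% | 60.0% | 95.7% |
| 5% | 37.1% | 57.0% | 93.7% |
| 10% | 35.1% | 54.0% | 91.3% |
| 12% | 34.3% | 52.8% | 90.2% |
| 15% | 33.2% | 51.0% | 88.3% |
| 20% | 31.2% | 48.0% | 84.9% |

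Power crosses 90% at about 12%. At 20%, restoring 90% would take 177 per arm.

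**The case against.** The strongest reply is that these calculations treat every early exit as a non-closer. Many section 7.2 exits (withdrawn consent, pregnancy, long hospitalisation, missed visits) need have nothing to do with healing. Suppose exits are unrelated to healing, 39% would close in either arm, and removal is 25% on Galnobax and 15% on SoC. The FAS test then holds 5.1%, while the all-randomised test with exits counted as failures shows 39%×0.75 = 29.3% against 39%×0.85 = 33.2% and rejects 11.3% of the time, mostly in favour of SoC.

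That arithmetic is right, but it answers a different question: what would have happened had nobody left. The protocol's endpoint is observed, confirmed closure. The scenario also removes subjects who close early, which the FAS rule does not allow.

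Further points have some force:

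- The arm splits are invented, and modest imbalance inflates the error little.
- The simulation uses a z-test, not the planned logistic model.
- Blinding of the assessing Investigator (section 6.3) limits exits driven by knowledge of the arm, though not exits caused by the treatment.
- Section 9.4.1 reports discontinuation reasons by group, so unequal loss would be visible. Seeing it does not correct the comparison.
- Given a six-assessment minimum, admitting early closers is sensible, since dropping them would be worse. The fault lies in pairing that clause with the minimum.
- The unseen SAP might add an all-randomised analysis. The protocol itself names none.

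The remedy does adopt a specific estimand, with exit without confirmed closure counted as failure. The plan should say so.

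**Conclusion.** The concern holds and should be corrected before unblinding; a set chosen afterwards would not be credible. The FAS depends on outcome by definition, failing ulcers can trigger the exits it discards, and PP does not bring those subjects back.

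The size depends on assumptions the documents cannot settle: how much of the 20% drop-out falls before six assessments, how it divides between arms, and how far it consists of non-closers. Balanced removal of non-closers costs no type I error but overstates closure rates and the risk difference. Unbalanced removal favours whichever arm loses more non-closers early: slight at 8/5, more than double the nominal error at 25/15. The direction cannot be predicted. Only exits before the sixth assessment are affected; later unhealed exits stay in the FAS.

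**What to change.** - **Primary set (4.2, 9.3, 9.4.1–9.4.3).** Use all subjects randomised to Groups 1 and 2, analysed as randomised. Do not substitute the ITT set, which omits never-dosed subjects. Count as not closed anyone without Target Ulcer Closure first observed by week 12 and confirmed as the protocol defines it, and state that this is the estimand.
- **Sensitivity.** Keep the present FAS and PP definitions as sensitivity analyses.
- **Section 9.4.9.** State that treatment failures remain in the primary set as not closed.
- **Section 9.2.** Say whether 39% and 60% are FAS or all-randomised rates. The current text randomises 300 "to ensure more than 90% power for the primary endpoint analysis"; restate power for 150 per arm as the range 84.9% to 95.7%.
- **Optional.** Ulcer status after exit can be used as supportive data, since section 7.1 already asks that "maximum possible and relevant Study information shall be gathered" for discontinued subjects.

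The cost is wording: no additional patients, visits or mandatory data, and no change to any treatment-stopping rule. The drawback is that power falls below the stated 90% if 39% and 60% are FAS rates and more than about 12% of randomised subjects are early non-closers. The sponsor should either accept that openly or revisit the sample size.
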